## APPENDIX E: TELEPHONE SCREEN

### Initial Phone Contact

#### Incoming call (Protocol 1 HP Member or Non-HP Member contacts SRC)

- ❖ Thank you for calling the TMD Self-Care Study. Before I describe the study I would like to start by asking how you heard about the TMD Self-Care Study.

1) How did you hear about the study? (*Do not read list— let the participant tell you, okay to check more than one if volunteered*)

- a) Brochure describe what brochure, where from, etc.: \_\_\_\_\_
- b) Clinic describe which clinic, etc.: \_\_\_\_\_
- c) Health Professional describe who, where, etc.: \_\_\_\_\_
- d) Friend describe: \_\_\_\_\_
- e) Recruitment letter describe: \_\_\_\_\_
- f) Other describe: \_\_\_\_\_
- g) Do not remember

#### Outgoing call (Protocol 2)

- ❖ Hello. May I please speak with [full name of potential participant]?  
*If respondent is not available, schedule a call back and end call.*  
*If respondent is on the phone, continue.*
- ❖ This is [INSERT FIRST NAME] from the HealthPartners Institute. I'm following up to a letter we recently sent you about a study that you may be able to participate in called the TMD Self-Care Study. Is now a good time to tell you more about this study?
- ❖ If no: When is a better time to reach you? (schedule a call back if possible, or thank them and end call)
- ❖ If Yes: Great! I'll need to ask you some question to determine your eligibility. But first, I would like to ask a few questions about you. This helps us understand who may or may not be interested in studies like the TMD Self-Care Study. We ask these questions of everyone before determining if they are eligible. These questions are not used to determine if you are eligible. **(Go to question 2)**

#### Messages

- ❖ Initial message: (Protocol 2)

Hello. This message is for [full name of respondent]. This is [INSERT FIRST NAME] from the HealthPartners Institute. I'm calling about a letter we recently sent about an exciting new research study. Please call us at [contact] to learn more. If you reach our voicemail,

please leave your full name, phone number and the best time to reach you. If we don't hear back, we'll try you again later. Thank you!

❖ Second (final) message:

Hello. This message is for [full name of respondent]. This is [INSERT FIRST NAME] from the HealthPartners Institute following up on a letter recently sent inviting you to participate in an exciting new research study. Sorry we missed you again. Please call us at [contact] if you are interested. We will not call you again unless we hear from you. Thank you!

- 2) How do you describe yourself? (check one)
  - a) Male
  - b) Female
  - c) Transgender
  - d) Do not identify as female, male, or transgender
- 3) What is your age? \_\_\_\_\_ (if less than 18 years old; not eligible)
- 4) Do you consider yourself to be Hispanic or Latino?
  - a) No, not Hispanic/Latino
  - b) Yes, Hispanic/Latino
- 5) Which of the following do you consider yourself (mark all that apply)?
  - a) White
  - b) American Indian/Alaskan Native
  - c) Asian
  - d) Native Hawaiian or Pacific Islander
  - e) Black or African American
  - f) Other (describe): \_\_\_\_\_
  - g) Don't know/refuse [do not read]

Thank you for answering these questions. Now I'll tell you more about the study.

**Study description:**

HealthPartners Institute is conducting a new study called TMD Self-Care Study that is funded by the National Institute of Health. The study is looking at a new way of helping people manage chronic pain from TMJ or temporomandibular muscle and joint pain, which is pain in the face and jaw.

The study will be randomizing people into one of two self-management online programs, the Personalized Activated Care and Training (PACT) program or the traditional care program. In the PACT program people will move through an eight week online course that includes audio, video and written materials along with phone coaching. In the traditional care program people will receive information about self-care of TMJ using video and written materials. Both groups will be asked to complete three surveys and will receive up to \$100 in Target gift cards for participation. This includes a \$20 gift card for completion of the initial survey, \$35 gift card for completing the survey at two months and \$45 gift card for completing the survey at four months.

6) Are you interested in seeing if you are eligible for this study?

a) No: Thank and end call.

b) Yes: continue

Great, I'll need to ask you some questions to determine your eligibility.

### Phone Screen for Study Eligibility

If at any time the caller **does not meet eligibility criteria** stop the screening, thank them for their interest, and refer to section “B” at the end of the screen. *Mark disposition as ineligible.*

7) Are you able and willing to access to the internet on a regular basis?

- a) NO ***If NO, go to section B***
- b) YES

***If asked, program is mobile responsive and can be accessed using cell phone or tablet.***

8) Are you able to read and speak in English?

- a) NO ***If NO, go to section B***
- b) YES

9) Will you be reachable by phone and able to participate in phone coaching calls if you are assigned to the PACT program?

- a) NO ***If NO, go to section B***
- b) YES

***These next questions are related to your TMD symptoms.***

10) Has a health professional ever told you that you have TMD/TMJ?

- a) NO ***If NO, go to section B***
- b) YES

11) In the last 30 days, which of the following best describes any pain in your jaw or temple area on either side?

- a) No pain (0 points)
- b) From very brief to more than once a week, but it does stop (1 point)
- c) Continuous (2 points)

12) In the last 30 days, have you had pain or stiffness in your jaw on awakening?

- a) No (0 points)
- b) Yes (1 point)

13) In the last 30 days, did the following activities change any pain (that is, make it better or make it worse) in your jaw or temple area on either side?

- a) Chewing hard or tough food
  - 1) No (0 points)
  - 2) Yes (1 point)
- b) Opening your mouth or moving your jaw forward or to the side

- 1) No
- 2) Yes
- c) Jaw habits such as holding teeth together, clenching/grinding, or chewing gum
  - 1) No
  - 2) Yes
- d) Other jaw activities such as talking, kissing, or yawning
  - 1) No
  - 2) Yes

14) How long have you experienced jaw or temple pain? (Check one)

- Less than 1 month
- 1 month or more but less than 3 months
- 3 months or more but less than 6 months
- 6 months or more but less than 1 year
- 1 year or more but less than 3 years
- 3 years or more

15) In the last 30 days, where did you have any jaw or temple pain? (Check yes or no for each)

Left jaw area	 Yes  No	Right jaw area	 Yes  No
Left temple area	 Yes  No	Right temple area	 Yes  No

[INSERT scoring information]

16) Are you currently participating in any other TMD/TMJ related studies?

- e) No
- f) Yes ***If YES, go to section B.***

17) Are you scheduled to have surgery for your TMD/TMJ disorder?

- g) No
- h) Yes ***If YES, go to section B.***

***Now I need to ask you a few additional medical questions.***

18) Do you have any serious medical conditions that might interfere with or prohibit you from participating in an online self-care program or currently pregnant?

- i) No

j) Yes ***If YES, go to section B.***

19) Have you received treatment for a mental health disorder or substance abuse in the past six months?

k) No

l) Yes ***If YES, go to section B.***

20)

#### **End Phone Screen – determine eligibility**

**If Questions 11, 12 and 13a = 2 or more then participant is eligible.**

**If Questions 11, 12 and 13a = less than 2 then participant is NOT eligible.**

**Yes/ No Eligible**

#### **A. Eligible**

Based on your responses, you are eligible for study participation. The next step would be for me to send you information about the study by email, including a study brochure and consent form. I will also send you instructions including a link to the study website with log-in information. You will then be directed to the study website to complete the consent form to enroll you in the study.

Would you like me to send study information to you so you can get started?

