## PROTOCOL SUMMARY

- Title:** Tailored Self-Management of TMD Pain using Health Information Technology
- Short Title** TMD Self-Care Study
- Précis:** This protocol describes activities to determine the feasibility and acceptability of proposed methods for a subsequent clinical trial of a tailored self-management program (PACT) designed to decrease pain in participants with temporomandibular disorders (TMD). The PACT program is a personalized program of exercise and behavioral changes implemented through a web-based program supported by a health coach. For this feasibility and acceptability study, 80 adults with TMD pain will be randomized either to the PACT program or to traditional self-care. This sample size was determined as the number needed to evaluate feasibility and acceptability of the primary intervention and determine the utility of the outcomes measures that will be collected at baseline, 8-week and 16-week follow-ups.
- Objectives:**
- Objective 1:** To evaluate the feasibility and acceptability of methods to conduct a full-scale multi-site randomized clinical trial comparing PACT self-management with traditional self-care for TMD. Methods to be tested are:
- a. Participant recruitment, consent, enrollment, and retention;
  - b. Participant adherence to the study;
  - c. Completion of study questionnaires at 8-week and 16-week follow-up;
  - d. Participant perceptions of the online website functionality and acceptability;
  - e. Participant perception of health coaches in the PACT program.
- Objective 2:** To demonstrate ability to accurately capture outcome measures to be used in the multi-site study.
- Objective 3:** To demonstrate ability to accurately capture potential mediators/moderators of specific behavioral and psychosocial factors on the PACT program's observed effects on pain and functioning outcomes through self-report. Hypothesized mediators are self-efficacy, participant activation exercise frequency and sleep quality. Hypothesized

moderators are disability status, catastrophizing, depression, repetitive strain from oral habits, perceived stress, and social support.

**Population:** The study will recruit 80 adults with TMD pain more than once a week from the HealthPartners Dental Group and selected dental clinics within the HealthPartners research network will be randomized. Ten participants will provide feedback on the online program during the development phase.

**Phase:** Pilot

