#### 3.2.3.2 Hypothesized moderators

Of the 80 patients participating in the study, we believe that 90% will complete the moderator measures at baseline and all follow-up periods and report the burden of completing these is acceptable. Specific measures of disability status, catastrophizing, depression, oral habits, perceived stress, and social support will be made by questionnaires, as described in section 8.1.1.

Outcome Measures including Data Constructs, Scales, Sources and intervals.								
	Construct	Scale/ Variable	Data Source	Target	Baseline	Intervention	Weeks from baseline	Weeks from baseline
Timing (weeks)					At Enrollment	0-8 wks.	8 wks.	16 wks.
Screening	Eligibility	DC-TMD Pain Screener and self-report criteria	Phone Screen	Potential participants screened	X			
	Demo-graphics	Age, marital status, education, employment,	Phone screen	Potential participants screened	X			

Outcome Measures including Data Constructs, Scales, Sources and intervals.								
	Construct	Scale/ Variable	Data Source	Target	Baseline	Intervention	Weeks from baseline	Weeks from baseline
Timing (weeks)					At Enrollment	0-8 wks.	8 wks.	16 wks.
Other Descriptive Information	Prior Medical Conditions	Prior Medical Conditions	On-line survey	Participants	X			
Objective 1 Process Evaluation	Recruitment	Contact/consent	Survey Center logs	Participants	X			
	Compliance/adherence	Self-report of intervention practice	On-line Survey	Participants		X		
	Compliance/adherence	Program evaluation form	On-line survey	Participants			X	
	Acceptability	Heuristic evaluation of ease of use and functionality	Web hits Survey	Participants			X	
	Participant experience	Barriers and facilitators to adherence	Qualitative interview	Participants		X	X	X
Objective 2 Primary Outcomes	Pain Severity	Graded Chronic Pain Scale-severity (7 items; of 10)	On-line survey	Participants	X	X	X	X
	Jaw Function	Jaw Functional Limitation Scale (JFLS-8; items; short version)	On-line survey	Participants	X	X	X	X
Objective 2 Secondary Pain Outcomes	Pain interference	Graded Chronic Pain Scale-intensity (3 items of 10)	On-line survey	Participants	X	X	X	X
Objective 3 Mediators	Self-efficacy	Chronic Pain Self-efficacy Questionnaire (5 item Self-efficacy for Pain management (PSE) scale)	On-line survey	Participants	X	X	X	X

Outcome Measures including Data Constructs, Scales, Sources and intervals.								

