## **5 STUDY ENROLLMENT AND WITHDRAWAL**

### **5.1 Subject Inclusion Criteria**

In order to be eligible to participate in this study, an individual must meet all of the following criteria:

- Age 18 or older
- Able and willing to access the internet on a regular basis
- Able and willing to participate in weekly phone coaching calls
- Able to read and speak English\*\*
- Willing and able to comply with all study procedures and be available for the duration of the study:
- Has a diagnosis of TMD pain using a self-report screener, specifically:
  1. Reporting pain in the jaw or temple area (on either side) in the last 30 days.
  2. Reporting pain or stiffness in the jaw on awakening in the last 30 days.
  3. Reporting changes in pain (either better or worse) in the jaw or temple area (on either side) in the last 30 days, after the following activities: chewing hard or tough food, opening the mouth or moving the jaw forward or to the side, jaw habits such as holding teeth together, clenching/grinding, or chewing gum, or other jaw activities such as talking, kissing, or yawning
- Has a frequency of TMD pain more than once a week with pain in the past 6 months
- Provides an electronically signed and dated informed consent form.

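### Unless the caller reports continuous pain, the Appendix E phone screen cannot establish the pain frequency that Section 5.1 requires

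*Protocol*

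**What the plan says.** Protocol Section 5.1 opens with "In order to be eligible to participate in this study, an individual must meet all of the following criteria". One bullet reads "Has a frequency of TMD pain more than once a week with pain in the past 6 months". Another requires a TMD pain diagnosis by self-report screener and lists three numbered items: recent jaw or temple pain, "Reporting pain or stiffness in the jaw on awakening in the last 30 days", and pain that changes with jaw activity. The Protocol Summary repeats the frequency: "The study will recruit 80 adults with TMD pain more than once a week". The outcome-measures table in Section 3.2.3.2 gives the phone screen as the data source for eligibility, with the scale "DC-TMD Pain Screener and self-report criteria".

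In Appendix E, Question 11 scores 0 for no pain, 1 for option b and 2 for continuous pain. Option b is worded "From very brief to more than once a week, but it does stop (1 point". Questions 12 (awakening) and 13a (chewing) score 0 or 1 each. Questions 13b to 13d carry no points. The decision rule is "If Questions 11, 12 and 13a = 2 or more then participant is eligible". A placeholder for scoring information earlier in the form is unfilled. A general instruction tells staff, when a caller fails a criterion, to "stop the screening, thank them for their interest, and refer to section" B, the ineligible script.

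**The concern.** The population is defined by pain frequency, and the phone screen is named as the source for eligibility. Yet the screen's one question that touches frequency merges callers below the required level with callers above it. Staff who follow the form exactly can tell a caller that he or she is eligible without learning whether the criterion is met.

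This matters even in a descriptive pilot. Feasibility is the primary outcome, and one target in Section 3.2.1 is that 80% of people who talk with staff are eligible. The multi-site trial would plan its recruitment on that percentage. Section 11.3 also requires the Annual Report to state whether all participants met the entry criteria. For a participant who chose option b, the printed screen cannot support that statement on frequency.

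**Working it through.** **Reading of the rule.** I take the cut-off as a sum, Q11 + Q12 + Q13a ≥ 2. It cannot mean 2 on each question, because Questions 12 and 13a have a maximum of 1.

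**Step 1: does anything else establish frequency?**
- Question 10 asks about a past diagnosis, Question 14 about duration and Question 15 about location. None asks how often.
- Section 6.1 says the criteria will be reviewed, but adds no frequency question.
- Section 6.2 requires unnamed baseline-questionnaire criteria to be negative before randomisation. It gives no frequency cut-off.
- The baseline survey (Appendix G, pain item 1) counts pain days in the last 30, with no eligibility threshold.
- The general stop instruction cannot act on option b, because that answer does not show that the caller fails.

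**Step 2: scored patterns.** There are 3 × 2 × 2 = 12 patterns (Q11, Q12, Q13a), and 8 reach 2 or more.

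| Q11 answer | Passing patterns | Number | Frequency criterion |
|---|---|---|---|
| No pain (0) | (0,1,1) | 1 of 4 | contradicted for the last 30 days |
| Option b (1) | (1,0,1), (1,1,0), (1,1,1) | 3 of 4 | unknown |
| Continuous (2) | (2,0,0), (2,0,1), (2,1,0), (2,1,1) | 4 of 4 | taken as met |

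The first row follows from the printed score alone. No stop is printed beside Question 11. If the first pain item in 5.1 is mandatory and staff apply the general stop, that caller is removed and 7 of the remaining 8 patterns pass.

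**Step 3: the score against the three pain items.** Adding 13b to 13d as yes/no multiplies each scored pattern by 2 × 2 × 2 = 8. That gives 96 patterns, of which 8 × 8 = 64 pass, or 7 × 8 = 56 without the no-pain callers. Counting the activity item as met by any of 13a to 13d, all three items are met in 2 × 1 × 15 = 30 patterns. All 30 score at least 2.

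| Reading of 5.1 | No-pain callers | Pass | Pass but do not meet 5.1 | Meet 5.1 but do not pass |
|---|---|---|---|---|
| All three required | excluded | 56 | 56 − 30 = 26 | 0 |
| All three required | included | 64 | 64 − 30 = 34 | 0 |
| Any two of three | excluded | 56 | 1 | 7 |
| Any two of three | included | 64 | 1 | 14 |

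Under the two-of-three reading, the 1 is continuous pain with every other answer negative. The 14 are (1,0,0) and (0,1,0), each with at least one of 13b to 13d positive: 7 + 7.

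**Step 4: would another cut-off do?** If all three items are required, a cut-off of 3 still passes 9 of the 96 patterns that fail 5.1 and rejects 7 that meet it. A cut-off of 4 passes none that fail but rejects 22 of the 30 that meet it. Changing the cut-off alone does not reproduce 5.1, and no cut-off below 4 excludes every option b caller.

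**The case against.** The best defence concerns the three pain items. The requirement to meet all criteria governs the bullets, and the three items sit inside a single bullet that describes a screener. They correspond to Questions 11, 12 and 13, so 5.1 may only describe the instrument while Appendix E supplies its decision rule. On that reading the score does not contradict the three items. This stands as a possible reading. A reader might infer from the 30-of-56 count that the score is plainly looser than 5.1, but the count depends on requiring all three items. Under a two-of-three reading, the rule mostly rejects callers who qualify.

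A reader might also infer that the Section 3.2.1 percentage will overstate eligibility. The documents do not settle the direction. Question 10 stops anyone never told by a health professional that they have TMD, and 5.1 has no such requirement. The percentage reflects that and the other stops as well as the score.

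A third tempting inference is that the 5.2 exclusion for major disc disorder requiring opioids goes unscreened. Question 17 covers surgery only, but item 20 is blank and may be that question, or text lost in reproduction. This is a query, not a finding.

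The impact is also softened. The pilot makes no efficacy test, recruitment works through diagnosis codes or clinic information and referral, and pain days are recorded before randomisation. None of this establishes frequency at the phone screen, so the core point is untouched.

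**Conclusion.** The frequency gap holds on the printed text. Section 5.1 sets a frequency, and the screen named as the eligibility source establishes it only through the continuous-pain answer. Three of four option b patterns pass with frequency unknown, and one no-pain pattern reaches the cut-off by score alone. This rests on reading the rule as a sum, on taking continuous pain as meeting the frequency, and on the form being used as printed.

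These are counts of answer patterns, not of patients. The documents give no answer frequencies, so the number of participants affected is unknown, and the pattern counts must not be read as proportions of enrolment. The gap should be corrected because it affects who is enrolled and what a primary feasibility measure describes. It does not invalidate the trial. The mismatch between the score and the three items remains a matter for reconciliation, with its direction open.

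**What to change.** 1. Add one item to Appendix E, with a stop, that tests the frequency criterion already in Section 5.1.
2. Compute the Section 3.2.1 eligibility percentage from the aligned screen.
3. Use the baseline pain-days item to report how many enrolled participants had infrequent pain. For orientation, once a week over 30 days is 30 / 7 ≈ 4.3 days. The match is approximate, because the item covers 30 days while 5.1 refers to the past 6 months.
4. Reconcile 5.1 with Appendix E on four matters: whether the three pain items are all required or only describe the screener that the score decides; the no-pain pass at Question 11; the Question 10 stop, which 5.1 does not contain; and the unfilled scoring placeholder. State in Section 6.2 which baseline criteria gate randomisation.
5. Confirm what blank item 20 was meant to ask.

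The cost is one more phone question and a wording amendment. The eligible percentage may fall. The frequency item adds no new entry rule, since it tests one that 5.1 already contains.

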#### **Yes:**

**Incoming calls:** Great, I will need to collect your contact information so I can email you study materials. If you have a few minutes, I would like to briefly review the study with you and answer any additional questions you may have while we are on the phone. Once you receive the email you can enter the website, review the consent form online, and get started.

**Outgoing calls:** Great, I will need to confirm the contact information we have for you. I will briefly review the study with you now while we are on the phone and answer any additional questions that might come up. In addition I will email you instructions for participation in the study including a study brochure, a link to the study website and your username/password to access the study website so you can complete the consent form to enroll into the study.

#### **No:**

I'm sorry to hear that. Would you mind telling me why? \_\_\_\_\_

#### **Thinking about it:**

Collect patient name only below to identify if they call back.

**Contact Information (auto-populated for outgoing calls)**

21) What is your full name? \_\_\_\_\_

22) What is your mailing address?

Address \_\_\_\_\_

City \_\_\_\_\_ State \_\_\_\_\_ Zip \_\_\_\_\_

23) What is your preferred method of contact, phone or email? If phone also obtain preferred time of day to contact:

a) Home phone ( ) \_\_\_\_\_

b) Work phone ( ) \_\_\_\_\_

c) Cell phone ( ) \_\_\_\_\_

d) Email address \_\_\_\_\_

24) Can we leave message at:

a) Home **YES NO**

b) Work **YES NO**

c) Cell **YES NO**

25) Are you able and willing to receive text messages?

a) **YES** (standards rates would apply; just know you won't be able to text us back)

b) **NO**

26) (If yes to any item in 25) May we call ourselves TMD Self-care Study when we call?

a) **YES**

b) **NO**

If NO: OK, is there any other name you would like us to use? \_\_\_\_\_

